## Follow-up

1) Information on general medical history and physical examination will be collected every 3 months for 3 years

2) Blood tumor markers of CEA (carcinoembryonic antigen) and CA19-9 (carbohydrate antigen 19-9) will be tested every 3 months for 3 years

3) Abdominal and pelvic ultrasound and chest X-ray examinations will be carried out every 3 months for 3 years

4) Abdominal and pelvic MRI or contrast enhanced CT scan will be done every year for 3 years

5) Colonoscopy will be performed within 1 year after surgery. If there is any abnormality, reexamination will be required within half a year. If no abnormality is found, once a year for 3 years. All new-found adenomas by the colonoscopy during follow-up are recommended to be resected.

6) Sexual function score is assessed by filling in the questionnaire (IIEF-5) both preoperatively and 1 year later since operation.

**Table 2.** International Index of Erectile Function-5 assessing sexual function

Over the past 6 months:					
1. How do you rate your confidence that you could get and keep an erection?	Very low 1	Low 2	Moderate 3	High 4	Very high 5
2. When you had erections with sexual stimulation, how often were your erections hard enough for penetration?	Almost never/never 1	A few times (much less than half the time) 2	Sometimes (about half the time) 3	Most times (much more than half the time) 4	Almost always/always 5
3. During sexual intercourse, how often were you able to maintain your erection after you had penetrated (entered) your partner?	Almost never/never 1	A few times (much less than half the time) 2	Sometimes (about half the time) 3	Most times (much more than half the time) 4	Almost always/always 5
4. During sexual intercourse, how difficult was it to maintain your erection to completion of intercourse?	Extremely difficult 1	Very difficult 2	Difficult 3	Slightly difficult 4	Not difficult 5

5. When you attempted sexual intercourse, how often was it satisfactory for you?	Almost never/never 1	A few times (much less than half the time) 2	Sometimes (about half the time) 3	Most times (much more than half the time) 4	Almost always/always 5
IIEF-5 scoring:					

The IIEF-5 score is the sum of the ordinal responses to the 5 items.

22-25: No erectile dysfunction

17-21: Mild erectile dysfunction

12-16: Mild to moderate erectile dysfunction

8-11: Moderate erectile dysfunction

5-7: Severe erectile dysfunction

7) 3-year tumor-free survival (month): The time from operation to confirmation of tumor's local recurrence or distant metastasis. The end point of the patient lost to follow-up is the date of loss. 30 days is defined as one month

8) 3-year overall survival (month): The time from operation to death. The end point of the patient lost to follow-up is the date of loss. 30 days is defined as one month

9) Stoma closure time (months since operation). Anal function is assessed by Wexner scale 3 months and 12 months after stoma closure, respectively.

**Table 3.** Wexner score assessing anal function

Type of Incontinence	Frequency				
	Never	Rarely	Sometimes	Usually	Always
Solid	0	1	2	3	4
Liquid	0	1	2	3	4
Gas	0	1	2	3	4
Wear Pad	0	1	2	3	4
Lifestyle altered	0	1	2	3	4

Never - 0

Rarely - Less than once a month

Sometimes - Less than once a week or once a month

Usually - Once a day or once a week

Always - Once a day or more

Score: 0 Perfect; 20 Complete Incontinence

(As to possible risks and benefits of participating in this trial, see details in the *informed consent document*.)

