### **Treatment**

If the participant matches with the requirements for this study and agrees to take part in it, once hospitalized, the participant will complete the established preoperative tests including blood routine, the comprehensive metabolic panel, blood coagulation function, tumor markers, blood type, infectious disease screening tests, chest, abdominal and pelvic CT (Computed Tomography) scan and MRI, colonoscopy, echocardiogram, pulmonary function, venous duplex ultrasound of legs. All male patients will be routinely asked to fill

in the IIEF-5 sexual function scoring questionnaire preoperatively.

The following comprehensive treatment will be depended on the examination results:

➤ **Neoadjuvant therapy**

The treatment plan will be made in accordance with the NCCN (National Comprehensive Cancer Network) Guidelines for Diagnosis and Treatment of Colorectal Cancer (Version 1.2021).

Neoadjuvant chemoradiotherapy: Pelvis radiotherapy with a total dose of 50 Gy with 25 courses in 5 weeks. Neoadjuvant chemotherapy include single drug therapy: capecitabine (CAP, 1250 mg/m^2, BID) or double drug therapy: oxaliplatin combined with capecitabine (CapeOX, oxaliplatin 130 mg/m^2, day 1, capecitabine 1000mg/ m^2, day 1 ~ 14, then rest for 7 days, repeated every 3 weeks) or three-drug therapy (mFOLFOX6, oxaliplatin 85 mg/ m^2 intravenous infusion for 2 hours, leucovorin calcium 400 mg/m^2 intravenous infusion for 2 hours, 5-FU (fluorouracil) 400 mg/m^2 intravenous infusion for 1 day, Then 1200 mg/ m^2/d×2 days of continuous intravenous infusion with a total of 2400mg/m^2 for 46 ~ 48 hours, repeated every 2 weeks.

Abdominal and pelvic MRI and contrast enhanced CT will be routinely performed 6 to 8 weeks after neoadjuvant therapy to confirm the extent of tumor regression without new-found distant metastasis. Those whose clinical stage after neoadjuvant therapy changes from T4 to T3 will be seen as eligible in this study.

➤ **Surgical treatment**

● Preoperative preparation

- 1) Patients older than 60 years old or having a smoking history for over 10 years will receive lung ventilation training and atomization treatment for 3 days
- 2) Intestinal preparation will be done with oral cathartic medications 12-24 hours before surgery
- 3) Prophylactic antibiotics will be given once anesthesia is begun, the second antibiotics will be given if the operation lasts for over 3 hours

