If the distal rectal transection cannot be done more than 1cm from the lower edge of the tumor, the anterior obturator nerve gateway approach will be used (that means the patient will be assigned to the experimental group). The steps are as follows: The peritoneum covering the ureter and external iliac artery is opened more than 2 cm across the vas deferens (male) or round ligament (female). The Retzius space and vesicohypogastric fascia are exposed. The obturator vessels and obturator nerve are properly identified. Care should be taken to avoid any injury when using energy devices near the obturator nerve. The gateway is then opened through the TME (total mesorectal excision) compartment and the lateral compartment. If necessary, an “endoloop” can be placed through the gateway, and the bundled S2-4 nerves, ureter and bladder vessels are gently retracted toward the cranial direction to widen the gap. The linear stapler is placed in the gateway to vertically transect the distal rectum. The following procedures are the same with the traditional group as described above.

During the operation, the following variables will be recorded: the angle between the linear stapler and the rectum, distance from the lower edge to the resecting margin, whether the operation converted to transanal approach, operative time, bleeding volume, anastomotic height from anal verge and the length of the stapling line.

➤ **Postoperative management:**

The following information will be recorded:

1) Vital signs (body temperature, pulse rate, respiration rate, blood pressure) are routinely monitored, gross volume of fluid input and output will be recorded every 24h, blood routine, the comprehensive metabolic panel and coagulation function tests will be performed every 3 days.

2) The time of catheter removal (days after operation), residual urine volume in the bladder will be measured by ultrasound examination. Whether there is a request to be re-catheterized or take oral medication to relieve the dysuria. All patients will be asked to fulfil the IPSS (International prostate symptom score) questionnaire to assess urinary function.

**Table 1.** International prostate symptom score assessing urinary function

In the past month:	Not at All	Less than 1 in 5	Less than Half the	About Half the	More than Half	Almost Always
--------------------	------------	------------------	--------------------	----------------	----------------	---------------

		Times	Time	Time	the Time	

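### The IIEF-5 form has no answer or scoring rule for men who attempted no intercourse in the recall period, so their scores are either capped at 13 or have no valid sum

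*Combined protocol and SAP*

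**What the plan says.** Follow-up, item 6, sets instrument and timing: "Sexual function score is assessed by filling in the questionnaire (IIEF-5) both preoperatively and 1 year later since operation". Under Treatment the preoperative form goes to every man ("All male patients will be routinely asked to fill"), and nothing restricts either assessment to sexually active men.

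Table 2 is headed "Over the past 6 months". Three of its five items presuppose intercourse or an attempt:

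- Item 3: "During sexual intercourse, how often were you able to maintain your erection after you had penetrated (entered) your partner"
- Item 4: "During sexual intercourse, how difficult was it to maintain your erection to completion of intercourse"
- Item 5: "When you attempted sexual intercourse, how often was it satisfactory for you"

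Every item has five printed answers coded 1 to 5, with no zero and no not-applicable answer. The total is the plain sum, read against bands that run from 5 to 25. Neither Follow-up nor Statistics says how blank items or inactive men are handled, and sexual activity is not among the recorded variables.

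Three other parts of the plan bear on this. The operating procedure for the experimental group includes an optional step in which "the bundled S2-4 nerves, ureter and bladder vessels are gently retracted toward the cranial direction to widen the gap". An ileostomy is routine in both groups, and its closure is recorded only as an outcome ("Stoma closure time (months since operation"). Statistics compares quantitative data with unadjusted two-group tests.

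**The concern.** The Objective includes postoperative functional outcomes, and the IIEF-5 is the only measure of sexual function. A dissection that may involve traction on the S2-4 nerves is one where erectile harm needs to be seen if it occurs and not reported if it does not.

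As printed, the score mixes two things: erectile function, and whether the man attempted intercourse at all in the past 6 months. The 1-year form covers about months 6 to 12 after surgery. Because activity is never captured, an analyst cannot later tell a man who tried and failed from one who did not try. The groups are formed by patient refusal and by intraoperative findings, so nothing in the design makes inactivity equal between them.

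**Working it through.** **Step 1. Reproduce the plan's own range.** Five items at the lowest code give 5 × 1 = 5; five at the highest give 5 × 5 = 25. This matches the printed bands (lowest 5-7, highest 22-25). So 1 is the lowest codable answer on every item, and the absence of a zero column is not a fault of text extraction.

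**Step 2. Scores open to a man with no attempts,** using Table 2's bands:

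| How he responds | Score | Printed band |
|---|---|---|
| Items 1-2 at 5, items 3-5 at 1 | 5+5+1+1+1 = 13 (the maximum) | Mild to moderate (12-16) |
| Items 2-5 at 1 | item 1 + 4 = 5 to 9 | Severe or moderate |
| Items 3-5 blank, remainder summed | at most 5+5 = 10 | At best moderate (8-11) |
| Items 3-5 blank, form void | none | Missing |

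He might also answer items 3-5 hypothetically. The plan does not say which of these applies.

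**Step 3. Largest error from items 3-5.** Three items can each be understated by at most 5 − 1 = 4 points, so 3 × 4 = 12, or equivalently 25 − 13 = 12. This is a ceiling per man, not a typical value.

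**Step 4. Spurious difference with no true effect.** If the error per inactive man is *e* in both groups and the inactive shares are f₁ and f₂, the mean difference is shifted by (f₂ − f₁) × *e*. The shares are assumptions; the documents give none.

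- Equal shares: 0.
- 20% versus 35%, *e* = 12: 0.15 × 12 = 1.8 points, the most possible from items 3-5 at those shares.
- 20% versus 35%, *e* = 6: 0.15 × 6 = 0.9 points.
- 20% versus 40%, if inactive men also mark 1 on item 2 and so score 5 to 9, against an assumed mean of 18 in active men: 0.20 × (18 − 9) = 1.8 to 0.20 × (18 − 5) = 2.6 points.

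**Step 5. Dilution when inactivity is equal.** A true effect *d* in active men shrinks to (1 − f) × *d*, while the spread widens. All inputs are assumed: 60 men per group, active mean 18 and SD 5, inactive mean 7 and SD 1.5, *d* = 3, two-sided 5% test. The SD of the mixture is √[f × 1.5² + (1 − f) × 5² + f(1 − f) × 11²].

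| Inactive in both groups | Difference | SD | Power |
|---|---|---|---|
| 0% | 3.0 | 5.00 | 91% |
| 20% | 2.4 | 6.31 | 55% |
| 40% | 1.8 | 6.70 | 31% |

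**Step 6. Cancellation.** On the same assumed means, take 40% inactive in control, 20% in the experimental group, and a true 3-point loss in experimental men. Control: 0.6 × 18 + 0.4 × 7 = 13.6. Experimental: 0.8 × 15 + 0.2 × 7 = 13.4. The 3-point loss appears as 0.2.

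**The case against.** The strongest reply is that the plan does not prescribe a wrong score; it leaves one undefined. That stands. A reader might infer that inactivity is always scored as erectile dysfunction, but a man who leaves blanks may simply become missing, and one who answers hypothetically may score normally.

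A reader might also infer that stoma or chemotherapy is what makes men inactive in months 6 to 12. The documents do not show this: no planned closure time and no total chemotherapy duration is given, so the overlap cannot be counted. The ileostomy is routine in both groups and the chemotherapy rules are common to both, so these influences may be largely shared. Shared inactivity dilutes a difference; it does not imitate one.

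Nor do the documents say that the nerves are retracted in every experimental patient. That step is taken only when needed, and its frequency is not stated.

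The size is also fairly disputed: 12 points is a ceiling, and 1.8 points applies that ceiling to every inactive man at one assumed pair of shares. The IIEF-5 is not among the Primary outcomes, it concerns men only, and the unadjusted non-randomised comparison already limits any causal reading.

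Finally, restricting the analysis to active men is no clean remedy. Activity at 1 year is observed after treatment and may itself be lost through nerve injury, so dropping inactive men could hide the harm being sought.

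What survives all of this is that the printed form has no place for an inactive man, every man receives it, and nothing recorded allows the gap to be repaired at analysis.

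**Conclusion.** The point holds as a defect of measurement and of scoring rules. Table 2 cannot represent a man with no attempts: marking 1 on items 3-5 gives him at most 13 and a dysfunction label, and leaving blanks gives no valid sum. That follows from the document's own scoring and needs no assumption.

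The effect on the group comparison is conditional and its size is unknown. Similar inactivity can dilute a real difference. Only unequal inactivity can create or cancel one; that is possible here but not demonstrated. The spurious difference runs from 0 (equal shares, equal error per man) to at most 1.8 points at an assumed 20% versus 35% with the full 12-point error. The power and cancellation figures are illustrations on assumed inputs.

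The change should be made for the functional and safety comparison. It does not affect the primary outcomes.

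**What to change.** 1. At both the preoperative and the 1-year assessment, add an answer for no sexual activity or no attempted intercourse, or a separate activity question, and ask the reason. Do not sum that answer as dysfunction.
2. Report the number of inactive men in each group as an outcome in its own right, with the reason and with stoma status. Stoma status over months 6 to 12 can be derived from the closure time already recorded.
3. Compare item 1, which any man can answer, in all men.
4. Present the five-item sum in active men only as a supportive analysis, stating that inactivity may itself result from nerve injury.
5. For forms already completed, fix before analysis how blanks and all-1 answers to items 3-5 are treated, and show a sensitivity analysis under the alternative treatments, such as scored as marked versus left unscored.

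The cost is a revised questionnaire page, a few data fields and a short scoring rule. Fewer men will contribute to the summed score. Forms already completed will lack the new answer; the stated start date (2020-12-01) precedes the protocol date (2021/9/7), so some preoperative forms may be affected. The handling rule can only bound the problem for those forms, not remove it.

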## Objective

To confirm the safety, feasibility and advantages by comparing the perioperative variables, postoperative functional and oncological outcomes of patients with ultralow rectal cancer treated by laparoscopic traditional distal rectal dissection vs. by transanterior obturator nerve gateway approach.

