### ➤ Exclusion criteria

- 1) The patient had previous abdominal surgery that will significantly infect the laparoscopic procedures;
- 2) Patients requiring emergency surgery owing to intestinal obstruction, perforation, or uncontrolled bleeding caused by tumor;
- 3) Patients with poor anal function preoperatively (Wexner score  $\geq 10$ );
- 4) ASA (American Society of Anesthesiologists) grading  $\geq IV$ ;
- 5) Pregnant patients;
- 6) Patients concomitant with severe mental illness;
- 7) The patient or the patient-authorized representative can't understand the contents and objectives of the study.

➤ **Withdraw criteria**

- 1) ISR cannot be performed by intraoperative evaluation and is replaced by Miles surgery;
- 2) Distant metastasis is confirmed intraoperatively or by postoperative pathological findings;
- 3) Patients had other primary tumors requiring surgical/drug treatment during the study, or had other illnesses that prevent the patient from continuing to participate this study;
- 4) Patients decide to withdraw from the study for any reason, or who are unable to complete the study because of any objective reasons.

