- 4) Urethral catheterization will be routinely done preoperatively
- 5) If the patient refuses to accept the novel approach before surgery, they will be directly enrolled in the traditional group. If both approaches are acceptable to the patient, the decision whether to use the novel approach will be made according to the intraoperative

conditions (see operating procedures below).

- Operating procedures

General anesthesia; Modified lithotomy position (Fig. 1a); Establishment of pneumoperitoneum: Place a trocar 1cm above the umbilicus through which to establish pneumoperitoneum and keep the abdominal pressure as 12 mmHg (millimeters of mercury).

Trocar placement: above the umbilicus (trocar C, 10 mm), upper right and left quadrants (trocars B and D, 5 mm), lower right quadrant (trocar A, 12 mm), lower left quadrant (trocar E, 5 mm), the midpoint between the pubic symphysis and umbilicus (trocar F, 5 mm).

[figure not shown]

Fig.1 Patient position and trocar placement

Abdominal exploration: Explore the abdominal cavity in accordance with the principle of non-contact, from far to near step by step, explore the tumor finally.

The mesosigmoid and mesorectum are dissected from the right lateral rectum towards the root of the inferior mesenteric artery (IMA). The IMA is transected and ligated, so is the inferior mesenteric vein. Posterior space of the descending colon is dissected following opening the peritoneum beside the left rectum. The rectum in the pelvis is mobilized from posterior rectal space, anterior rectal space to bilateral rectal space successively. The lower edge of the tumor is marked by a clamp. The linear stapler is placed in the pelvis to clamp the distal rectum below the tumor to see if the transection can be done more than 1cm from the lower edge of the tumor. If yes, the distal rectum will be transected by the traditional approach (that means the patient will be assigned to the traditional group). The proximal bowel is transected through a small midline incision. Then the coloanal

anastomosis will be done intracorporeally. A surgical drain is placed in the pelvis and a terminal ileostomy is routinely performed. All incisions are closed.

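### The anal-function comparison is conditional on stoma closure and unadjusted, and the plan does not say how patients whose stoma is not closed are counted

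*Combined protocol and SAP*

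**What the plan says.** All references are to the combined protocol.

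- **Who has a stoma.** Under Treatment, operating procedures: "A surgical drain is placed in the pelvis and a terminal ileostomy is routinely performed". For the experimental group, after the new transection step: "The following procedures are the same with the traditional group as described above". Every patient who completes the planned operation in either group is therefore meant to have a stoma.
- **When continence is scored.** Follow-up, item 9: "Anal function is assessed by Wexner scale 3 months and 12 months after stoma closure, respectively". The same item records the time to stoma closure in months from operation. It gives no rule for a stoma that is never closed, and no summary of the proportion closed.
- **Baseline.** Exclusion criterion 3 removes "Patients with poor anal function preoperatively", defined as a Wexner score of 10 or more. The score has no other stated preoperative use.
- **Analysis.** The Statistics section names the t test and Mann-Whitney U test for quantitative data. It mentions no adjustment, no missing-data rule and no analysis population for functional outcomes.
- **Role of function.** The Objective includes "postoperative functional and oncological outcomes of patients with ultralow rectal cancer". Wexner is not among the listed primary outcomes.

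**The concern.** The set of patients with a Wexner score is fixed by an event after surgery. If closure depends on how the operation went, the scored patients are a selected part of each group, and selection need not be equal in the two groups.

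Unequal selection is plausible here for two reasons. First, the groups are not randomised. Patients who decline the new approach go to the control group, and the others are assigned by whether the stapler can transect more than 1 cm below the tumour. The groups can therefore differ in anatomy or tumour position. Second, leakage is a primary outcome, and the Background argues that the manner of transection affects it. If leakage delays or prevents closure, a comparison restricted to closed patients conditions on something the approach may change.

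What is at stake is any statement on continence. Anus preservation is the rationale for the new approach. A stoma that stays defeats that purpose, yet it leaves no trace in the planned Wexner comparison. The unadjusted test also leaves out a baseline that eligibility screening requires.

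**Working it through.** **1. Is there a figure to reproduce?** No. The Sample size section gives 100 experimental and at least 100 control patients, without alpha, power, effect size, SD or dropout. No closure rate and no Wexner mean or SD appears anywhere. The figures below are illustrations on stated assumptions.

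**2. Who lacks a score.** Follow-up runs to 3 years (36 months) after operation.
- Never closed: no score.
- Closed after month 36 − 12 = 24: no 12-month score within follow-up.
- Closed after month 36 − 3 = 33: no score at all within follow-up.

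By contrast, sexual function (Follow-up, item 6) is scored before surgery and 1 year after operation, so it has a baseline and a clock that starts at surgery. Anal function has neither in the plan for comparison.

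**3. What a closed-only comparison can hide.** Assume a mean of 8 among closed patients in both groups. Code non-closure as 20, the maximum in Table 3. Let u be the share unclosed.

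All-patient mean = (1 − u) × 8 + u × 20. The difference between groups is therefore 12 × (difference in u).

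| Unclosed, group A vs B | All-patient means | Difference | Closed-only difference |
|---|---|---|---|
| 10% vs 10% | 9.2 vs 9.2 | 0 | 0 |
| 5% vs 10% | 8.6 vs 9.2 | 0.6 | 0 |
| 5% vs 15% | 8.6 vs 9.8 | 1.2 | 0 |
| 10% vs 20% | 9.2 vs 10.4 | 1.2 | 0 |

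For example, 0.95 × 8 + 0.05 × 20 = 8.6 and 0.85 × 8 + 0.15 × 20 = 9.8. The sign follows whichever group has more unclosed stomas.

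**4. Selection among the closed patients themselves.** Assume a normally distributed latent continence score whose correlation with the tendency to stay unclosed is ρ. The mean among closed patients shifts by −ρ × φ(z) / (1 − u) SD, where z is the 1 − u quantile. At 5% versus 15% unclosed:
- ρ = 0.3: −0.033 vs −0.082, a difference of about 0.05 SD.
- ρ = 0.5: −0.054 vs −0.137, a difference of about 0.08 SD.

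Both favour the group with more unclosed stomas, and both are small. In these illustrations the main problem is that unclosed stomas are not counted at all.

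**5. Loss of precision.** Assume two-sided alpha 0.05 and 80% power. The detectable difference is √(2/n) × (1.96 + 0.84) SD. This gives 0.40 SD at n = 100 per group and 0.44 SD at n = 80 (20% unclosed). Precision is not the issue.

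**6. Adjustment for baseline.** Residual variance is multiplied by 1 − r², where r is the correlation of the preoperative with the later score: 1 at r = 0, 0.91 at r = 0.3, 0.75 at r = 0.5. The documents give no r. Exclusion 3 confines the baseline to scores below 10, which tends to lower r. The gain in precision is therefore uncertain. The firmer reason to adjust is baseline imbalance between non-randomised groups.

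**The case against.** The strongest reply is that a continence score means little while the bowel is diverted, so scoring after closure is the sensible choice. That is correct. A reader might infer that the timing is the error, and the documents do not support that. Closure time is also a recorded follow-up item, so the number unclosed in each group could be recovered. That too is correct, but the plan commits to no such summary and does not tie it to the Wexner comparison.

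A reader might also infer that function is compared in the better-healed patients, or that the plan favours the new approach. Neither can be shown. The documents do not say how often or why stomas remain, and the groups may not differ. The 0.6 and 1.2 points rest wholly on assumed closure shares and on coding a stoma as 20, which Table 3 labels complete incontinence rather than diversion.

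It may further be tempting to define success as a closed stoma with Wexner below 10 at a fixed time from operation, using data in hand. The plan schedules no score at a fixed time from operation, and it uses 10 only as a preoperative exclusion limit. Reasons for non-closure are not listed as collected.

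Finally, one baseline score will not remove confounding that arises from assignment by feasibility. That stands, and it limits what adjustment can be claimed to do.

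What survives all of this is the missing rule for unclosed patients and the missing adjustment.

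**Conclusion.** The concern holds in a limited form. The planned Wexner comparison is conditional on stoma closure, is unadjusted between non-randomised groups, and has no rule for patients not closed or closed too late to be scored. The size and direction of any bias cannot be known from the documents. There is none if scores among closed patients and the share unclosed are both equal across groups. On the assumptions shown, unclosed shares that differ by 5 to 10 percentage points hide 0.6 to 1.2 points.

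The weight is moderate. Function is part of the stated objective but Wexner is not a primary outcome. The change should be made before the functional data are analysed, because a later choice of how to count unclosed stomas could be guided by the results.

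**What to change.** 1. Keep the Wexner comparison in closed patients, state that it is conditional on closure, and adjust it for the preoperative Wexner score, for example by ANCOVA. Do not present the adjustment as removing all confounding.
2. Report the proportion with a closed stoma by group at a fixed time from operation, using the recorded closure times.
3. Add a supportive analysis in all patients who had the sphincter-preserving resection. Rank them by the scheduled 12-month post-closure Wexner score, and give the worst rank to those not closed in time to have that score within the 3-year follow-up. State in advance how deaths and withdrawals are handled. The ranks can be compared with the Mann-Whitney test already named.

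**Cost.** A paragraph of analysis text and one extra analysis of closure times and scores that the plan already schedules. The preoperative Wexner score must be obtained for exclusion 3, but it is not in the list of preoperative assessments under Treatment, so the case report form should hold its numerical value. If the sponsor also wants reasons for non-closure, that needs a new data field.

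**Downside.** The ranked analysis mixes stoma status with continence, so the closure proportion and the scores among closed patients must be shown beside it.

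### The Wexner frequency anchors in Table 3 overlap at once a day and leave two categories loosely bounded, so the same symptoms can be scored one point apart per item

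*Combined protocol and SAP*

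**What the plan says.** Table 3 in the Follow-up section lists five items (solid, liquid, gas, pad wearing, altered lifestyle), each scored 0 to 4. The total is anchored as "Score: 0 Perfect; 20 Complete Incontinence". Below the table the categories are defined in words. *Never* is 0, and the other four are:

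- score 1: "Rarely - Less than once a month"
- score 2: "Sometimes - Less than once a week or once a month"
- score 3: "Usually - Once a day or once a week"
- score 4: "Always - Once a day or more"

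The scale is the trial's measure of bowel continence after surgery: "Anal function is assessed by Wexner scale 3 months and 12 months after stoma closure". The Objective names postoperative functional outcomes among the comparisons to be made. A Wexner score also decides eligibility: item 3 of the Exclusion criteria removes "Patients with poor anal function preoperatively", defined as a score of 10 or more. No other section defines the frequency categories more precisely.

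**The concern.** A scoring rule should send each reported frequency to exactly one score. These anchors do not. Once a day belongs to two categories. *Sometimes* can be read as having no floor, in which case it takes in everything that *Rarely* covers. *Usually* gives two frequencies and does not say that those in between belong to it.

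The study is multi-center, and the protocol gives no rule for resolving a tie between categories. Raters must settle the wording themselves. At follow-up that adds measurement noise to the comparison of anal function. At screening, if the same anchors apply, it could decide whether a borderline patient is enrolled.

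**Working it through.** **Inputs.** Five items, each scored 0 to 4, and the four anchors quoted above (Follow-up, Table 3); exclusion at a total of 10 or more (Exclusion criteria, item 3).

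**The plan's own figure.** 5 items × 4 points = 20, which matches the stated maximum.

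**Scores allowed at each frequency.** The middle column takes the words literally. The right column takes *Sometimes* as monthly up to less than weekly, and *Usually* as a range from weekly to daily.

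| Frequency | Literal | Ordinary reading |
|---|---|---|
| Never | 0 | 0 |
| Below monthly | 1 or 2 | 1 |
| Monthly to below weekly | 2 | 2 |
| Weekly | 3 | 3 |
| Above weekly, below daily | none | 3 |
| Once a day | 3 or 4 | 3 or 4 |
| More than once a day | 4 | 4 |

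The ordinary reading closes the gap and removes the lower overlap. It does not remove the overlap at once a day.

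**Size on the total.** If k items sit at an overlapping frequency, the total can vary by k × 1 = k points. The ceiling is k = 5. With all five items once a day, the total is 5 × 3 = 15 or 5 × 4 = 20. One, two or three such items give a range of 1, 2 or 3 points.

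**Effect at the cut-off of 10, ordinary reading.** Three items once a day and two never gives 3 × 3 = 9 up to 3 × 4 = 12. More generally, let k items be once a day and let the other 5 − k items sum to S. The total can fall on either side of 10 when 3k + S ≤ 9 and 4k + S ≥ 10, that is, when 10 − 4k ≤ S ≤ 9 − 3k:

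- k = 1: S = 6 from four items. Seven patterns: 4+2, 4+1+1, 3+3, 3+2+1, 3+1+1+1, 2+2+2, 2+2+1+1.
- k = 2: S = 2 or 3 from three items. Five patterns: 2, 1+1, 3, 2+1, 1+1+1.
- k = 3: S = 0. One pattern, the 9-to-12 example.
- k = 4 or 5: none, because the total is already at least 12.

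That is 7 + 5 + 1 = 13 patterns. With six frequency levels there are C(10, 5) = 252 unordered five-item patterns, so 13 of 252 can straddle the cut-off. Under the literal reading, leaving aside the frequencies that it assigns to no category, the count is 39 of 252. These are counts of possible answer patterns, not proportions of patients; the documents give no distribution of Wexner scores.

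**After correction.** With bands that do not overlap and leave nothing out, every frequency has one score, and the range due to wording is 0.

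**The case against.** The strongest reply is that trained raters will read the list as an ordered scale. *Rarely* names less-than-monthly symptoms exactly, so nobody need score them as *Sometimes*; doing so would make score 1 redundant. *Usually* is clumsy wording for the band between weekly and daily. On that reading only one frequency is ambiguous. Five points then requires every item to be at exactly once a day and two raters to choose oppositely on all five.

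Most of this stands. A reader might infer from the literal text that a patient with less-than-monthly symptoms on all five items scores 5 or 10, and so is eligible or excluded depending on the rater. That example depends on the strained reading of *Sometimes* and should not carry the point.

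It is also fair to say that the link to screening is an inference. Table 3 appears only under Follow-up, the exclusion criterion does not refer to it, and the preoperative work-up in the Treatment section names the IIEF-5 but no Wexner form.

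What survives is the once-a-day overlap. It remains on every reading, and once a day is a natural answer for an item such as pad wearing.

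**Conclusion.** The anchors are a defective stated rule, and the defect is modest in size. The certain part is a one-point ambiguity for each item reported at once a day. The loosely bounded *Sometimes* and the two-point *Usually* add to it if raters take the words literally. The ceiling is 5 of 20 points, and the usual effect should be smaller. The consequence is avoidable noise in the anal-function comparison at both follow-up times. The documents give no standard deviation or expected difference for the Wexner score, so the noise cannot be expressed as a loss of precision or power.

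An effect on eligibility follows only if the Table 3 anchors are also used at screening. On the ordinary reading it then involves a range of at most 3 points.

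Two stronger conclusions are tempting and are not supported. A reader might infer that the group comparison is biased. That would need centres to read the anchors differently and also to use the two approaches at different rates, and the documents show neither. A reader might also infer that the main result is at risk. The Wexner score is not among the Primary outcomes, and the stated group sizes are not tied to it, so any effect there could come only through a few borderline eligibility decisions.

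**What to change.** Replace the definitions under Table 3 with bands built from the protocol's own cut points of month, week and day:

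- *Never* (0): no occurrence.
- *Rarely* (1): some occurrence, but less than once a month.
- *Sometimes* (2): at least once a month but less than once a week.
- *Usually* (3): at least once a week but less than once a day.
- *Always* (4): once a day or more.

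State in the Exclusion criteria that the preoperative score uses this same table, and use one version at screening and at both follow-up assessments. The exclusion threshold itself need not change for this purpose.

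The stated start date (2020-12-01) precedes the protocol date (2021/9/7), so some forms may already be complete. Re-score these only where the actual frequency was recorded. Table 3 provides for category scores and not for frequencies, so some early forms may not be recoverable. Flag those, and repeat the Wexner comparison without them as a sensitivity check.

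The cost is one corrected table in the protocol and case report form, plus a review of completed forms. No treatment or primary outcome changes.
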